## 10.8. Analysis of immunogenicity

The primary and secondary immunogenicity analyses will be based on the PPS. If the difference between PPS and FAS is greater than 10%, a second analysis based on the FAS will be performed to complement the PPS analysis.

Titers below the LLOQ will be handled based on the assay procedure and will be described in the statistical analysis plan.

One of the main objectives of the study is to estimate the extent of a potential immune interference, due to immunological stress to lymph nodes in the arm where the combination vaccine is administered in comparison to injections in 2 different arms of individual vaccines. The sample size defines the conditions under which the observed

reduction in immune response will be attributed to a true lymph-node effect or is the consequence of natural variability. An acceptable probability of falsely detecting the lymph-node effect was set to 10% (1-sided test). The minimum probability of detecting the lymph node is set to 80%.

#### Criteria for the Statistical Test

rMenBOMV+ACWY\_S will be declared statistically inferior if the 2-sided 80% confidence intervals (CIs) of the ratio of the GMT with rMenBOMV+ACWY\_D as control is lower than 1. The lymph-node effect would therefore be the most probable cause for the decrease observed.

#### Analysis of hSBA GMT

An analysis of covariance (ANCOVA) model will be used to analyze post-vaccination log-transformed titers of hSBA for both the primary and secondary objectives (i.e. the hSBA at 1 month after the last vaccination and the hSBA at 1 month after the first vaccination, respectively). The ANCOVA model will be fitted to each serogroup/strain individually, and in addition the serogroup B strains will be grouped together to perform a pooled analysis. The GMTs obtained through the ANCOVA model will be called “adjusted” and the “unadjusted” GMTs will be obtained through descriptive statistics. Unadjusted and adjusted GMTs and associated 2-sided 80% CIs will be computed for each study group and for each strain at each visit. The fixed-effect model will include the age strata, treatment, serogroup, and center as fixed effects. The pre-vaccination log-transformed titer with centering at zero will be included as a continuous covariate. An interaction between serogroup and pre-vaccination log-transformed titer centered at zero will be included in the model. For each study group, adjusted GMTs and their 80% CIs will be obtained by exponentiating (base 10) the least squares means and the lower and upper limits of the 80% CIs of the log-transformed titers (base 10).

The following contrasts will be computed to investigate possible effects on the immune response based on strains common to each treatment group:

- a. rMenBOMV+ACWY\_S versus rMenBOMV+ACWY\_D (test for immune interference, due to immunological stress to lymph node)
- b. MenABCWY versus rMenBOMV+ACWY\_S (test for other unknown immunological interference)
- c. rMenBOMV+ACWY\_S versus rMenBOMV
- d. rMenBOMV+ACWY\_S versus MenACWY
- e. rMenBOMV+ACWY\_D versus rMenBOMV
- f. rMenBOMV+ACWY\_D versus MenACWY
- g. MenABCWY versus rMenBOMV
- h. MenABCWY versus MenACWY

In addition, the distribution of antibody titers for each strain will be displayed using reverse cumulative distribution curves.

**Analysis of Percentage of Subjects With Titers Above LLOQ and a 4-fold Increase**

The percentage of subjects with titers above the LLOQ and a 4-fold increase as well as the associated 2-sided 80% Clopper-Pearson CIs will be computed by study group at each visit [Clopper, 1934]. In addition, differences in percentages and 2-sided 80% CIs between the groups will be calculated and the associated CI for the difference will be constructed using the method of Miettinen and Nurminen [Miettinen, 1985].

Unadjusted and adjusted GMTs and associated 2-sided 80% CIs will be computed for each group and for each strain at each visit. For each study group, adjusted GMTs and their 80% CIs will be obtained by exponentiating (base 10) the least square means and the lower and upper limits of the 80% CIs of the log-transformed titers (base 10).

The fixed-effect model for the individual serogroups/strains will include the age strata, treatment, and center as fixed effects. The fixed-effect model for the pooled analysis will include the age strata, treatment, strain, and center as fixed effects. The pre-vaccination log-transformed titer with centering at zero will be included as a continuous covariate. An interaction between serogroup and pre-vaccination log-transformed titer centered at zero will be included in the model.

Additionally, the group GMT ratios will be computed. The 2-sided 80% CIs for the group GMT ratio will be constructed by exponentiating the group difference of the least squares means of the log-transformed titers and the lower and upper limits of the 80% CI.

## **10.9. Analysis of safety**

The analysis will be based on the Safety Sets.

### **10.9.1. Analysis of extent of exposure**

The frequency and percentage of exposed subjects will be summarized overall and by study group.

### **10.9.2. Analysis of local and systemic adverse events**

All solicited AEs will be summarized according to defined severity grading scales (see [Table 12](#)).

Frequencies and percentages of subjects experiencing each AE will be presented for each symptom severity. Summary tables showing the occurrence of any local or systemic AE overall and at each time point will also be presented. Local AEs will be assessed according to which vaccine was administered and the site of administration (e.g. upper or lower deltoid and the arm used for administration).

Post-vaccination solicited AEs reported from day 1 to day 7 will be summarized for the intervals days 1 to 3, days 4 to 7, and days 1 to 7 by maximal severity and by study group, excluding the 30-minute post-vaccination measurement, which will be summarized separately. In addition, solicited AEs ongoing after day 7 will be presented as unsolicited AEs.

Body temperature will be classified as  $<38^{\circ}\text{C}$  (no fever) and  $\geq 38^{\circ}\text{C}$  (fever), as well as by  $0.5^{\circ}\text{C}$  increments from  $36.0^{\circ}\text{C}$  up to  $\geq 40^{\circ}\text{C}$ .

Erythema, induration, and swelling will be categorized as none (<25 mm), 25 to 50 mm (mild), 51 to 100 mm (moderate), and >100 mm (severe local reactions). The severity of pain will be categorized as none, mild (transient with no limitation in normal daily activity), moderate (some limitation in normal daily activity), and severe (unable to perform normal daily activity).

If an AE occurs more than once for a subject, it will be counted in the summary only once, according to the maximal severity. Summary tables showing the occurrence of any local or systemic AEs overall will be presented.

### **10.9.3. Analysis of other adverse events**

#### Unsolicited Adverse Events

This analysis applies to all AEs occurring during the study, judged either as probably related, possibly related, or not related to vaccination by the investigator, recorded in the Adverse Events eCRF, with a start date on or after the date of first vaccination. Adverse events starting prior to the first vaccination will only be listed. The original verbatim terms used by investigators to identify AEs in the eCRFs will be mapped to preferred terms using the MedDRA dictionary. The AEs will then be grouped by MedDRA preferred terms into frequency tables according to system organ class.

All reported AEs, as well as AEs judged by the investigator as at least possibly related to study vaccine(s), will be summarized according to system organ class and preferred term within system organ class. These summaries will be presented by study group and by interval of study observation. When an AE occurs more than once for a subject, the maximal severity and strongest relationship to the study group will be counted.

Separate summaries will be produced for the following categories:

- SAEs
- AEs that are possibly or probably related to vaccine(s)
- AEs leading to withdrawal
- AEs leading to a medically attended visit
- AESI

Data listings of all AEs will be provided by subject. In addition, AEs in the categories above will be provided as listed data.

### **10.10. Interpretation of analyses**

All analyses will be descriptive.

## 10.11. Conduct of analyses

Any deviation(s) or change(s) from the original statistical plan outlined in this protocol will be described and justified in the final study report.

### 10.11.1. Sequence of analyses

The final study analysis will only be performed when all data up to the end of the study will be available and cleaned. Individual data listings will be provided and a clinical study report will be written.

*Any outcome of exploratory testing will be reported in an annex/addendum to the final study report. (Amended 29 Aug 2018)*

### 10.11.2. Statistical considerations for interim analyses

Not applicable.

## 11. ADMINISTRATIVE MATTERS

To comply with ICH GCP administrative obligations relating to data collection, monitoring, archiving data, audits, confidentiality, public disclosure requirements and publications must be fulfilled.

### 11.1. Electronic case report form instructions

A validated PPD defined electronic data collection tool will be used as the method for data collection.

In all cases, subject initials will not be collected nor transmitted to PPD. Subject data necessary for analysis and reporting will be entered/transmitted into a validated database or data system. Clinical data management will be performed in accordance with applicable PPD standards and data cleaning procedures.

While completed eCRFs are reviewed by a PPD Site Monitor at the study site, omissions or inconsistencies detected by subsequent eCRF review may necessitate clarification or correction by the investigator or appropriately qualified designee. In all cases, the investigator remains accountable for the study data.

The investigator will be provided with an electronic format in read only mode of the final version of the data generated at the investigational site once the database is archived and the study report is complete and approved by all parties.

### 11.2. Subject diary

Subject Diaries will be the only source document allowed for solicited local and systemic AEs (including body temperature measurements), starting after the initial 30-minute post-vaccination period at the clinic. The following additional rules apply to documentation of safety information collected in the Subject Diary.

The investigator or delegated staff should monitor the Subject's Diary status throughout the study for compliance and any solicited local and systemic AEs that were of concern to the subject.

- No corrections or additions to the information recorded by the subject/parent(s)/LAR(s) within the Subject Diary will be allowed after it is delivered to the site.
- Any blank or illegible fields on the Subject Diary must be described as missing in the eCRF.

The following additional rules apply to documentation of Subject Diary information collected in the eCRFs:

The site must enter all readable entries in the Subject Diary into the eCRF, including those values that may be biologically implausible (e.g. body temperature: 400°C).

Any illegible or implausible data should be reviewed with the subject/parent(s)/LAR(s). If an underlying solicited or unsolicited AE is described on review with the subject, this should be described in the source document and reported as an unsolicited AE in the Adverse Event eCRF (e.g. if the subject above confirms body temperature of 40°C on the day in which body temperature: 400°C was written into his/her Subject Diary, this fever of 40°C should be recorded in the Adverse Event eCRF).

Any newly described safety information (including a solicited AE) must not be written into the Subject Diary and must be described in the study file as a verbally reported AE. Any AE reported in this fashion must be described as an unsolicited AE and therefore entered on the Adverse Event eCRF.

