### Missing Data

For safety analyses, subjects who missed reporting symptoms (solicited or unsolicited) or concomitant medications will be analyzed to determine the missing mechanism. For the analysis of solicited symptoms, implausible measurements will not be replaced but they will be excluded from the analyses. Missing values will not be imputed for solicited/unsolicited AEs or concomitant medications.

In order to minimize the effect of missing data, the study period will be divided into time intervals for the safety analyses. For unsolicited AEs, the study period will be divided into the following intervals: all unsolicited AEs reported from day 1 to day 31 after vaccination (day of vaccination = day 1, Visit 1 and Visit 3 will be assessed separately and combined), medically attended AEs reported during the entire study period, AEs leading to premature withdrawal from the study during the entire study period, SAEs reported during the entire study period and AESI reported during the study period for the Unsolicited Safety Set.

Concomitant medications will be assessed for the entire study period for the Overall Safety Set.

Solicited AE data will be analyzed by the following intervals: 30 minutes post-vaccination on day of vaccination, 1 – 3 days post-vaccination (including the day of vaccination as day 1, excluding 30 minutes post-vaccination), 4 days – 7 days post-vaccination, and 1 day - 7 days (including the day of vaccination as day 1, excluding 30 minutes post-vaccination). Intervals will be assessed for Visit 1 and Visit 3, separately and combined, for the Solicited Safety Set. Solicited local AEs will be considered separately by vaccine for study groups where two vaccinations are administered at each visit, and also separately by location

A subject will be classified as having missing data within the specified intervals as described below:

- Solicited AEs
  - Temperature will be regarded as missing if “Temperature taken” = “No” at every time point within the interval (on Post-vaccination Body Temperature eCRF page).
  - Pain will be regarded as missing if no intensity values are recorded for Vaccine A and Vaccine B separately at every time point within the interval (on Vaccine A/Vaccine B Solicited Local Adverse Event eCRF pages). An intensity value of ‘None’ is a valid value and will not be considered a missing value.

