#### Implausible Values for Vital Signs and Solicited Adverse Events

The following numeric values will be considered implausible and will be excluded from summaries:

- Erythema: values less than 0 mm or equal to or greater than 500 mm
- Induration: values less than 0 mm or equal to or greater than 900 mm
- Temperature: values less than or equal to 33.0°C or equal to or greater than 42.0°C.

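### SAP 4.3 sets no implausibility limit for swelling, and a fever confirmed after its diary value is excluded can drop out of the solicited fever table

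*Protocol*

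**What the plan says.** **Data entry (Protocol 11.2).** "The site must enter all readable entries in the Subject Diary into the eCRF, including those values that may be biologically implausible"; the protocol's example is 400°C. No correction to the diary "will be allowed after it is delivered to the site". A reaction that comes to light when an implausible entry is reviewed with the subject is to be "reported as an unsolicited AE in the Adverse Event eCRF". In the example, where the subject confirms 40°C, "this fever of 40°C should be recorded in the Adverse Event eCRF".

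**Exclusion (SAP 4.3).** Under Missing Data, "implausible measurements will not be replaced but they will be excluded from the analyses". The list of implausible values has three items: erythema (below 0 mm, or 500 mm and above), "Induration: values less than 0 mm or equal to or greater than 900 mm", and "Temperature: values less than or equal to 33.0°C or equal to or greater than 42.0°C". Swelling is not on it.

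**Grading (SAP 9.1.1 and Table 8; Protocol 10.9.2).** Swelling is a solicited local event and shares its scale with erythema and induration: none below 25 mm, severe above 100 mm. Fever is 38°C or more, and temperature is also tabulated in 0.5°C bands up to 40°C and above. Each subject counts once per interval, at maximal severity.

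**Missingness and denominators (SAP 4 and 4.3).** "Temperature will be regarded as missing if" the temperature-taken item is answered No at every time point of the interval. By default the denominator is all subjects of the group in the analysis set. It is reduced only if at least 20% of subjects have no data and the Fisher test across groups gives p<0.05.

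**The concern.** The protocol deliberately lets impossible values into the database and leaves it to the SAP to screen them out. That works only if the screen covers every numeric solicited item and the SAP says what becomes of a subject after a value is removed. Swelling fails the first condition and temperature the second.

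The errors run in opposite directions: an impossible swelling value inflates the severe cell, and a confirmed high fever can be absent from the fever cell. Both cells are likely to be sparse, so one subject shows. Protocol 1.3.1 names fever as an important identified risk of rMenB+OMV NZ, one of the study vaccines.

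The refiling also fits poorly with the endpoint, which is the occurrence of solicited events in the 7 days from vaccination (Protocol 10.2, SAP 3.2.2). The protocol glossary makes a solicited symptom unsolicited when its onset lies outside the solicited period. Here the onset is inside it.

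**Working it through.** Neither document states a figure to reproduce. The check applies the written rules to example entries. The values 400°C and 40°C are the protocol's; all others are assumed for illustration.

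**1. Local reactions.** Rule: exclude a value x if x < 0 or x ≥ L, with L = 500 mm for erythema, L = 900 mm for induration and no limit for swelling. Otherwise grade 0 if x < 25, grade 1 for 25–50, grade 2 for 51–100, grade 3 (severe) if x > 100.

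| Diary entry | Erythema | Induration | Swelling |
|---|---|---|---|
| 120 mm | severe | severe | severe |
| 700 mm | excluded | severe | severe |
| 5000 mm | excluded | excluded | **severe** |
| −5 mm | excluded | excluded | **grade 0** |

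Under the maximal-severity rule, one entry of 5000 mm makes the subject a severe swelling case for the whole interval, whatever the other days show.

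**2. Temperature.** Rule: keep t if 33.0 < t < 42.0, take the maximum of the kept values, and call it fever if that maximum is ≥ 38°C.

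| Seven diary days | Maximum of valid readings | Solicited table |
|---|---|---|
| A. 400 on one day, 36.8 on the other six | 36.8 | no fever |
| B. 400 on one day, 38.6 on another, 36.8 otherwise | 38.6 | fever, but below the ≥40°C band |
| C. 400 the only reading | none | not defined |
| D. As A, with the confirmed 40.0 in place of 400 | 40.0 | fever, ≥40°C band |

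The gap between A and D is the under-count. In A the subject is not missing under SAP 4.3, because temperature was taken, so the subject remains in the denominator. In C the subject is not missing either, for the same reason, yet has no usable value and no rule assigns a class.

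**3. Where the confirmed fever goes.** It is on the AE form, so it enters the unsolicited tables by system organ class, preferred term and severity (SAP 9.1.2). It also enters the combined solicited and unsolicited table for 30 days after vaccination, which leaves out SAEs. Neither table has temperature bands or the Days 1–3, 4–7 and 1–7 intervals, so neither corrects the solicited fever table.

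**4. Size.** One subject is 100/n percentage points:
- n = 100: 100/100 = 1.0
- n = 95: 100/95 = 1.05

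With k affected subjects in a group of 100, the shift is k points. The documents give no basis for k, and it may be zero.

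**The case against.** The strongest defence is that Protocol 11.2 is a deliberate source rule. The diary is the sole permitted source for solicited reactions after the first 30 minutes, and anything recalled later is kept apart as unsolicited. Folding recalled events into the solicited tables would mix two sources. This stands, and is why the diary-only table should remain the main one. It does not remove the need to show how many confirmed reactions that table omits.

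It can also be said that the general sentence in SAP 4.3 excluding implausible measurements already covers swelling. It cannot be applied as written, since a programmer has no number to use.

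Several stronger readings are tempting, and the documents do not support them:

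- *A confirmed 40°C fever is always tabulated as no fever.* Nothing recodes the value; 400°C is excluded. No fever results only in the solicited temperature table, and only if every other valid reading in the interval is below 38°C (case A, not B). The event itself is not lost from the report.
- *All solicited reactions are affected.* The exclusion limits apply only to erythema, induration and temperature. Pain, nausea, myalgia, arthralgia, headache and fatigue are graded categories, so no numeric limit removes them.
- *The different limits for erythema (500 mm) and induration (900 mm) are an error.* They are unexplained, but nothing requires them to match or says which is right. A common limit is a preference.
- *The effect is 2 points in an age stratum of 50.* No planned solicited table is split by age stratum, and Protocol 10.5.7 intends no subgroups.

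**Conclusion.** The swelling gap is a plain omission. As written, the rules tabulate an impossible swelling value as severe, while an entry such as 5000 mm is dropped for erythema and induration.

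The fever point is real but conditional. Solicited fever, including the 40°C and above band, can be under-counted when an excluded value is later confirmed and the subject's remaining valid readings are below 38°C. A subject with no other reading has no defined class.

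The size is about 1 percentage point per affected subject in a group of about 100. This assumes that such diaries occur at all, and their number is unknown. Safety is a secondary objective, the analyses are described as descriptive, and the primary immunogenicity results do not change. It is a small defect, worth correcting because the correction costs little.

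**What to change.** In SAP 4.3 and 9.1.1:

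1. Add swelling to the list of implausible values with stated numeric limits. If these differ from the limits for erythema or induration, give the reason.
2. Keep the diary-only solicited tables as the main analysis. Add a supplementary row or footnote that counts solicited-type reactions confirmed on the AE form with onset on Days 1–7 after vaccination, at the confirmed value, and label it as combining diary and recalled reports.
3. State that a subject with no valid reading left in an interval after exclusions is missing for that symptom, and show the subject in the Missing row that SAP 4 already provides for categorical summaries.

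Setting only the single excluded day to missing would not help. Exclusion already has that effect, and the maximum over the remaining days stays the same.

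The cost is a few lines of SAP text and a little programming. The data are already on the AE form, so nothing new is collected. The one drawback is the mixed sources in the supplementary row, which the label addresses.

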### **11.3. Study monitoring**

PPD will monitor the study to verify that, amongst other items, the:

- Data are authentic, accurate, and complete.
- Safety and rights of subjects are being protected.
- Study is conducted in accordance with the currently approved protocol, any other study agreements, GCP and all applicable regulatory requirements.

The investigator and the head of the medical institution (where applicable) agrees to allow the monitor direct access to all relevant documents.

The investigator must ensure provision of reasonable time, space and qualified personnel for monitoring visits.

Direct access to all study-site related and source data is mandatory for the purpose of monitoring review. The monitor will perform a eCRF review and a Source Document Verification. By Source Data Verification we understand verifying eCRF entries by comparing them with the source data that will be made available by the investigator for this purpose.

The Source Documentation Agreement Form describes the source data for the different data in the eCRF. This document should be completed and signed by the site monitor and investigator and should be filed in the investigator's study file. Any data item for which the eCRF will serve as the source must be identified, agreed and documented in the source documentation agreement form.

Upon completion or premature discontinuation of the study, the monitor will conduct site closure activities with the investigator or site staff, as appropriate, in accordance with applicable regulations, GCP, and PPD procedures.

